To answer the primary research question, we will compare the rates of quitting among smokers randomized to ENDS vs. those receiving usual care, on an intention-to-treat basis. Continuous smoking cessation from target quit date will be the main outcome, confirmed by biomarkers of exposure (exhaled carbon monoxide (CO), urinary cotinine, anabasine and NNAL).[1] We will calculate quit rates, relative risks (RR), and absolute risks for ENDS +SCC (intervention group) compared to SCC alone (control group). We will further compare groups using multivariate regression models adjusting for appropriate co-variables. Participants lost during follow-up will be categorized as ongoing smokers in the intention-to-treat analysis. We intend to obtain full follow-up data on all randomized participants (see Follow-up and Retention). Participants who stopped smoking, and who are ongoing ENDS users, will be considered quitters. We will present per-protocol analyses in sensitivity analyses given that participants in the control group might start using ENDS in the first six months.

We will repeat these calculations for the secondary smoking cessation outcomes such as alternate definitions of the outcome of having quit smoking: a.) <5 cig from target quit date and b.) 7-days point abstinence (no cigarettes within the 7 days before outcome assessment)).

To test the effect of ENDS on reducing the number of cigarettes smoked per day, we will define a binary predictor of $\geq 50\%$ smoking reduction from baseline to follow-up smoking and repeat the analyses for the main outcome of quitting. We will also use joint multivariate random-effects (JMRE) models allowing to model CPD and smoking cessation. In addition, we will use mixed linear effect model to analyze the change in CPD modelled as a continuous outcome over time.

We will compare the proportion of adverse events and serious adverse events between groups using recommended methods. For the measures of changes in measures of urinary biomarkers, exhaled breath measures, CVRFs and respiratory symptoms from baseline to the 6-months visit, we will first compare the changes in these measures between the intervention and control group using two-sample t-tests or Wilcoxon rank-sum test, whenever appropriate. We will then fit univariate and multivariate mixed linear effect models. We will use multivariate linear and multinomial logistic regression models to compare groups according to their exposure to tobacco smoking and ENDS.

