Study Centre(s):	Five sites in Switzerland including University Hospitals Bern, Geneva, Lausanne, Zürich and St. Gallen.

Statistical Considerations:
	
Sample size:
 
Based on the results of a systematic review and meta-analysis of previous trials, we expect a RR of smoking cessation of 1.6; based on our experience with RCTs in the setting of smokers willing to quit and contacting health care professionals to seek help receiving SOC alone, we expect a 12% quit rate in the control group and thus 19% in the intervention group (ENDS + SOC) (7% absolute difference in abstinence rate). With a two-sided alpha of 0.05 and a power of 90%, we will include a minimum 557 smokers per group, for a total of 1114 smokers, to find a significant difference in quit rates. Previous experience suggests we should assume a 5% loss to follow-up, so we will increase our sample size by 5% (59 smokers). We will thus recruit 1172 smokers. We will consider participants lost to follow-up to be continuing smokers, and our primary analysis will be intention-to-treat. Though participants in the control group will not be actively provided with ENDS and asked not to use ENDS during the first 6 months of the study, we expect that 5% will still purchase ENDS on their own. The sample size of the entire trial is based on the primary outcome; the power to find a statistically significant difference for secondary outcomes is limited to the total number of participants.
 
Efficacy analysis:
 
To answer the primary research question, we will compare the rates of quitting among smokers randomized to ENDS vs. those receiving SOC, on an intention-to-treat basis. Continuous smoking cessation from target quit date will be the main outcome, confirmed by urinary anabasin levels.¹ We will calculate quit rates, relative risks (RR), and absolute risks for ENDS + SOC (intervention group) compared to SOC alone (control group). We will further compare groups using multivariate regression models adjusting for appropriate co-variables. Participants lost during follow-up will be categorized as ongoing smokers in the intention-to-treat analysis. We intend to obtain full follow-up data on all randomized participants (see Follow-up and Retention). Participants who stopped smoking, and who are ongoing ENDS users, will be considered quitters. We will also present per-protocol analyses given that some participants in the control group might start using ENDS in the first six months.
 
We will apply the same data analysis methods for the secondary smoking cessation outcomes such as: a.) <5 cig from target quit date and b.) 7-days point prevalence abstinence (no cigarettes within the 7 days before outcome assessment)).
 
To test the effect of ENDS on reducing the number of cigarettes smoked per day, we will define a binary predictor of $\geq 50\%$ cigarettes per day of reduction (cpd) from baseline to follow-up. We will also use joint multivariate random-effects (JMRE) models allowing to model CPD and smoking cessation. In addition, we will use mixed linear effect model to analyze the change in CPD modelled as a continuous outcome over time.
 
We will compare the proportion of adverse events and serious adverse events between groups using recommended methods. As to changes in measures of urinary biomarkers, exhaled breath measures, CVRFs and respiratory symptoms from baseline to the 6-, 12- and 24-months visit, we will first compare the changes in these measures between the intervention and control group using two-sample t-tests or Wilcoxon rank-sum test, whenever appropriate. We will then fit univariate and multivariate mixed linear effect models. We will use multivariate linear and multinomial logistic regression models to compare groups according to their exposure to tobacco smoking and ENDS.

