5.2 Secondary Outcomes

The secondary outcomes are as follows:

- Secondary smoking cessation outcomes:

6 month follow-up:

- Continuous smoking abstinence. Self-report of having smoked no cigarettes from TQD, validated by urinary levels of NNAL (4-(methylnitrosamino)-1-(3-pyridyl)-1-butanol). If NNAL is missing, validation by urinary levels of anabasine or exhaled CO.
- Self-reported smoking abstinence allowing a 2-week 'grace period' after the TQD
- Validated smoking abstinence allowing a 2-week 'grace period' after the TQD, validated by urinary levels of anabasine. If anabasine is missing validation by exhaled CO.
- Validated smoking abstinence allowing a 2-week 'grace period' after the TQD, validated by urinary levels of NNAL. If NNAL is missing, validation by urinary levels of anabasine or exhaled CO.
- Self-reported smoking abstinence allowing up to 5 cigarettes in total after the TQD.
- Validated smoking abstinence allowing up to 5 cigarettes in total after the TQD, validated by urinary levels of anabasine. If anabasine is missing validation by exhaled CO.
- Validated smoking abstinence allowing up to 5 cigarettes in total after the TQD, validated by urinary levels of NNAL. If NNAL is missing, validation by urinary levels of anabasine or exhaled carbon monoxide (CO).
- Self-reported 7-day point prevalence abstinence at 6 months, Self-report of having smoked no cigarettes in the past seven days.
- Validated 7-day point prevalence abstinence. Confirmation of having smoked no cigarettes in the past seven days, validated by urinary levels of anabasine. If anabasine is missing validation by exhaled carbon monoxide (CO).
- Validated 7-day point prevalence abstinence. Confirmation of having smoked no cigarettes in the past seven days, validated by urinary levels of NNAL. If NNAL is missing, validation by urinary levels of anabasine or exhaled carbon monoxide (CO).
- Number of cigarettes smoked per day (CPD), self-reported, at baseline, TQD, phone visits and 6 months visit
- Change in number of cigarettes smoked per day (CPD), self-reported. Successful reduction defined as 50% reduction in CPD.
- Concentrations of urinary TSNAs (NNN, NNK and its metabolite NNAL), VOCs and PAHs (1- and 2-Naphtol and 1-OHP)
- Respiratory symptoms assessed by questionnaire (CAT, mMRC, ACT, ECRHS) ¹³⁴⁻¹³⁷
- Oxidative stress assessed by 8-OHdG and 8-isoprostane concentrations in both EBC and urine

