11.4.3 Secondary Analyses

We will repeat the calculations described in 11.4.2 for the secondary smoking cessation outcomes. To test the effect of ENDS on reducing the number of cigarettes smoked per day, we will define a binary predictor of >50% smoking reduction from baseline to follow-up smoking and repeat the analyses for the main outcome of quitting. We will also use joint multivariate random-effects (JMRE) models allowing to model CPD and smoking cessation. In addition, we will use mixed linear effect model to analyze the change in CPD modelled as a continuous outcomes over time.

We will present modified per-protocol sensitivity analyses, in particular for participants in the control group who might have started using ENDS in the first six months.

For the measures of changes in measures of urinary biomarkers, exhaled breath measures, CVRFs and respiratory symptoms and pulmonary function from baseline to the 6-months visit, we will first compare the changes in these measures between the intervention and control group using two-sample t-tests or Wilcoxon rank-sum test, whenever appropriate. We will then fit univariate and multivariate mixed linear effect models. We will use multivariate linear and multinomial logistic regression models to compare groups according to their exposure to tobacco smoking and ENDS.

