urinary level of NNAL (<10 pg/ml creat) OR	To be defined	To be defined	To be defined	{ y < 10 if y!=missing, x<3 if y==missing & x!=missing, vs_co2_level<10 if y==missing & x==missing & vs_co2_level!=missing }	
urinary level of anabasine (<3 ng/ml) OR	To be defined	To be defined	To be defined		
CO level	Vital, Vital_6m	vs_co2_level	continuous		
Self-reported 7-day point prevalence abstinence at 6 months	cig_ecig_6m	quit_smoke_again, quit_smoke_7days	Binary: No, Yes	quit_smoke_again == No AND quit_smoke_7days == No	Binary
Self-reported 7-day point prevalence abstinence at 6 months AND	cig_ecig_6m	quit_smoke_again, quit_smoke_7days	Binary: No, Yes Binary: No, Yes	{ quit_smoke_again == No AND quit_smoke_7days == No} AND { x < 3 if x!=missing, vs_co2_level<10 if x==missing & vs_co2_level ==missing}	Binary
urinary level of anabasine (<3 ng/ml) OR	To be defined	To be defined	To be defined		
CO level	Vital, Vital_6m	vs_co2_level	continuous		
Self-reported 7-day point prevalence abstinence AND	cig_ecig_6m	quit_smoke_again, quit_smoke_7days	Binary: No, Yes	{quit_smoke_again == No AND quit_smoke_7days == No} AND	Binary
urinary level of NNAL (<10 pg/ml creat) OR	To be defined	To be defined	To be defined	{y < 10 if y!=missing, x<3 if y==missing & x!=missing, vs_co2_level<10 if	
urinary level of anabasine (<3 ng/ml) OR	To be defined	To be defined	To be defined		

CTU Bern	SAP for: ESTxENDS	Version: 4.02.0
----------	-------------------	---------------------------------

CTU Bern	Template: Statistical Analysis Plan (SAP)	Version: 03
	Code: CS_STA_TEM-11	Valid from: 28.02.2019 5.6.2023

CO level	Vital, Vital_6m	vs_co2_level	continuous	y==missing & x==missing & vs_co2_level!=missing}	
Number of cigarettes smoked per day (CPD)	cig_ecig / cig_ecig_6m	quit_more1perday	continuous (number of cigarettes per day in the last 7 days)	[BL, TQD, phone visits and 6-month visit] quit_more1perday	Continuous
Change in the self-reported number of cigarettes smoked per day in the last 7 days	cig_ecig / cig_ecig_6m	quit_more1perday	continuous (number of cigarettes per day in the last 7 days)	(quit_more1perday[month 6] / quit_more1perday[day 0]) >= 0.5 IF [month 6]{contact_estab_yn == Yes AND quit_smoke_again == Yes AND quit_smoke_7days == Yes AND quit_smoke_nperday == ">=1x/Tag"} ELSE TRUE	Binary
CAT	cat / cat_6m	q1 to q8	radio (0 to 5)	sum(q1 to q8)[cat_6m] – sum(q1 to q8)[cat]	continuous (score scale 0-40, difference can be 0-40 as well)

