6.5 Missing data

Missing values in the primary outcome will be categorized as persistent smokers. We intend to obtain full follow-up data on all randomized participants.

Missing data in secondary smoking cessation outcomes will be treated as the primary outcome. If more than 5% of data is missing, all other secondary outcomes will be imputed, assuming values to be missing at random. Each outcome will be imputed separately to ensure robust imputation models. We will use all baseline variables (see Table 2) and outcome measures at all time points as predictors in the imputation models. The two intervention groups will be imputed separately. Variables with more than 50% missing values will not be used for the imputation model. Binary variables with a frequency of less than 5% in one category will be omitted from the predictors, levels of categorical variables with a frequency of less than 5% in one category will be combined with another level in a sensible way. Continuous variables will be log-transformed if it improves normality (checked by Shapiro-Wilks test and QQ plots). If predictors are too highly correlated among each other, we will only consider the predictor which is more strongly correlated with the outcome. In case of missing baseline covariates, ~~W~~we will use multiple imputation by chained equation. We will impute values using predictive mean matching for continuous and ordinal variables, logistic regression for binary variables, and a multinomial regression model for categorical variables with more than two levels. In total, fifty imputed data sets will be generated, which will be analysed as described using Rubin's rules (Rubin 1987). We will compute stabilized inverse probability of censoring weights to take into account potentially informative censoring or outcome data.

CTU Bern	SAP for: ESTxENDS	Version: 4.02.0
----------	-------------------	------------------------

CTU Bern	Template: Statistical Analysis Plan (SAP)	Version: 03
	Code: CS_STA_TEM-11	Valid from: 28.02.2019 5.6.2023

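### Protocol 9.0 gives two success thresholds for the cigarette-reduction outcome, and the SAP 2.0 derivation rule neither settles them nor codes a reduction

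*Supplement*

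**What the plan says.** Protocol 9.0, synopsis (Statistical Considerations, efficacy analysis): "we will define a binary predictor of $\geq 50\%$ cigarettes per day of reduction (cpd) from baseline to follow-up". This carries over the inclusive sign of the Protocol 2.0 synopsis ("we will define a binary predictor of $\geq 50\%$ smoking reduction from baseline to follow-up smoking").

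Protocol 9.0, section 11.4.3: "we will define a binary predictor of >50% smoking reduction from baseline to follow-up smoking". The stated purpose is to test the effect of ENDS on the number of cigarettes smoked per day (CPD). The same section also plans a joint model of CPD and cessation and a mixed linear model of continuous CPD.

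Protocol 9.0, section 5.2, and SAP 2.0, section 6.1: "Successful reduction defined as 50% reduction in CPD", with no inequality sign.

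SAP 2.0, section 6.2, Table 3: the row for change in CPD is TRUE when "quit_more1perday[month 6] / quit_more1perday[day 0]) >= 0.5". This test applies only to participants who were contacted at month 6, have smoked again, smoked in the last 7 days, and smoke at least once a day. The row ends "quit_smoke_nperday == '>=1x/Tag'} ELSE TRUE".

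SAP 2.0, section 6.5: "Missing data in secondary smoking cessation outcomes will be treated as the primary outcome", meaning that missing counts as persistent smoking. Protocol section 9.2.2 lists the CPD reduction among the secondary smoking cessation outcomes, so this rule covers it.

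**The concern.** A listed secondary outcome has no single success rule. The protocol's two thresholds disagree for anyone who exactly halves consumption. The SAP derivation, where one would look for the answer, describes something else.

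A second issue is interpretation. A quitter has a 100% reduction, and Table 3 makes abstainers successes. The comparison introduced to test an effect on cigarettes per day therefore contains the whole cessation effect. A reader could take a significant result as evidence that participants who kept smoking cut down, when it need not show that.

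**Working it through.** **1. The texts side by side, for a participant going from 20 to 10 CPD.**
- Protocol 9.0 synopsis (≥50%): success.
- Protocol 9.0 section 11.4.3 (>50%): failure.
- Protocol 5.2 and SAP 6.1 (50%): not determined.
- SAP Table 3, taking day 0 as 20: ratio 10/20 = 0.5, TRUE. But 20 to 20 (ratio 1.0) is also TRUE, and 20 to 5 (ratio 0.25) is not. The row cannot serve as the tie-breaker.

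**2. The other parts of the Table 3 row.**
- *Reference.* The text says baseline; the row uses day 0, the target quit date. The variable covers the last 7 days and the baseline visit is at day −7, so the day-0 value describes the week after randomisation, when the intervention arm already has devices.
- *Everyone else TRUE.* This takes in abstainers, non-daily smokers whatever they smoke, and participants not reached. The last group contradicts section 6.5.
- *Reversing the label does not help.* If TRUE meant failure, the inequality would make sense, but abstainers would then be failures.

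**3. The plan's own figure.** Inputs from Protocol 11.2: 12% v 19%, two-sided 5%, 90% power. Unpooled formula: n = (1.960 + 1.282)² × (0.12 × 0.88 + 0.19 × 0.81) / 0.07² = 10.51 × 0.2595 / 0.0049, which gives 557 per group, as stated. The planned size is 586 per group.

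**4. Cessation carried into the reduction outcome.** Let q be the quit rate and r the share of continuing smokers who meet the reduction criterion. The value of r is an assumption and is set equal in both arms. Success = q + (1 − q)r, so the difference is 0.07 × (1 − r). Power is for a two-sided 5% test with 586 per arm.

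| r | Control | ENDS | Difference (points) | RR | Power |
|---|---|---|---|---|---|
| 0 | 12.0% | 19.0% | 7.0 | 1.58 | 91% |
| 0.1 | 20.8% | 27.1% | 6.3 | 1.30 | 72% |
| 0.3 | 38.4% | 43.3% | 4.9 | 1.13 | 40% |
| 0.5 | 56.0% | 59.5% | 3.5 | 1.06 | 23% |

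No row contains any effect among continuing smokers.

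**5. Effect of the cut-off.** Let h be the share of continuing smokers at exactly 50% (assumed; not in the documents). With r = 0.3 under ≥, the strict sign leaves r − h.

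| h | Control | ENDS | RR | Power |
|---|---|---|---|---|
| 0 (that is, ≥) | 38.4% | 43.3% | 1.13 | 40% |
| 2% | 36.6% | 41.7% | 1.14 | 42% |
| 5% | 34.0% | 39.3% | 1.15 | 46% |
| 10% | 29.6% | 35.2% | 1.19 | 54% |

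A larger share would move it further. At h = 20% the strict sign leaves r = 0.1, the RR 1.30 row in step 4, in the same direction.

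**6. Table 3 read literally.** Assume 5% not reached per arm, every continuing smoker daily, nobody exactly at 0.5, and day 0 equal to baseline. Contacted continuing smokers are 1 − 0.12 − 0.05 = 0.83 and 1 − 0.19 − 0.05 = 0.76. At r = 0.3:
- Literal success: 1 − 0.83 × 0.3 = 75.1% v 1 − 0.76 × 0.3 = 77.2%.
- Reducers as successes, missing as failures: 0.12 + 0.83 × 0.3 = 36.9% v 0.19 + 0.76 × 0.3 = 41.8%.

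At r = 0.5 the literal rule gives 58.5% v 62.0%: recorded success falls as more people reduce.

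**The case against.** Counting quitters as reducers is a usual convention for a binary outcome in all randomised participants, because a 100% reduction is a reduction. Protocol section 4.2 names quitting or reducing in one objective, so the combined measure fits that wording. Cessation is reported separately, CPD is its own outcome, and section 11.4.3 adds two CPD models. SAP section 7 explains why they are absent from the SAP: further analyses are left to the investigator. All of this stands, and it means that including quitters is not an error. It does not supply a threshold or mend Table 3, and SAP 2.0 specifies neither model.

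A reader might also infer that the result hinges on the cut-off. The documents do not support that. Only exact halvers change class, their number is not given, and any clustering of reports on round numbers is an assumption. Across the shares tried, the success rates and RR move but the direction does not.

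One could call the Table 3 inequality a slip for a reduction of at least 0.5. That is plausible, and would favour the inclusive sign. It would still leave the day-0 reference and the coding of people not reached.

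**Conclusion.** The point holds as an unresolved definition. Protocol 9.0 contradicts itself on the threshold, and SAP Table 3 is unusable as written: its inequality is reversed for continuing daily smokers, its reference is day 0, and it counts people not reached as successes against section 6.5. The size of the threshold effect is unknown. With r = 0.3 and 2–10% exact halvers, both assumed, the RR goes from 1.13 to 1.14–1.19.

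Separately, the planned quit rates alone produce 7 × (1 − r) points of difference (4.9 at r = 0.3 and 3.5 at r = 0.5, with r assumed equal between arms). The binary result by itself is therefore not evidence of reduction without quitting. This part calls for better reporting. The outcome is secondary, so the primary comparison is unaffected.

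**What to change.** 1. Use one cut-off throughout: write ≥50% in Protocol section 11.4.3 to match the synopsis, and carry the sign into section 5.2 and SAP 6.1.
2. Rewrite the Table 3 row: success is month-6 CPD / baseline CPD ≤ 0.5. Abstainers are successes, non-daily smokers are classified by their actual consumption, and missing is failure as in SAP 6.5. SAP 6.2 suggests that a numeric count is held only for those smoking more than once a day, so the rule for non-daily smokers must be written out.
3. Add a descriptive table for all randomised participants: abstinent; still smoking with ≥50% reduction; neither. Read it as a whole. The middle category alone is (1 − q)r, which is lower in the arm with more quitters even with no effect in continuing smokers: 24.3% ENDS v 26.4% control at r = 0.3, and 40.5% v 44.0% at r = 0.5.

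The cost is a few lines of text, one derivation to reprogram and one table from data already collected. The downside is that the combined reduction figure has to be interpreted more cautiously.

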1.6 Data Safety Monitoring Committee

Not applicable.

1.7 Any other relevant Committee, Person, Organisation, Institution

Data management

CTU Bern, Faculty of Medicine, University of Bern
[name], [name], Switzerland
[contact]

Study Steering Committee

The study steering committee will be responsible for the overall supervision of the trial and will regularly meet to discuss scientific and logistic aspects of the trial. The study steering committee consists of 5 persons, one person from each center involved in the study.

2. ETHICAL AND REGULATORY ASPECTS

Before the study will be conducted, the protocol, the proposed patient information and consent form as well as other study-specific documents will be submitted to a properly constituted Competent Ethics Committee (CEC) in agreement with local legal requirements, for formal approval. Any amendment to the protocol must as well be approved (if legally required) by these institutions.

The decision of the CEC concerning the conduct of the study will be made in writing to the Sponsor-Investigator before commencement of this study. The clinical study can only begin once approval from all required authorities has been received. Any additional requirements imposed by the authorities shall be implemented.

